1. INTRODUCTION

1.1. Disease Background

[figure not shown]
Non-alcoholic fatty liver disease (NAFLD) is the most common chronic liver disease in the world, with a global prevalence estimated to be 24% (Younossi, 2018). When steatosis is accompanied by evidence of liver cell injury and cell death, as well as inflammation, it is considered to be nonalcoholic steatohepatitis (NASH). More advanced stages of NASH are accompanied by fibrosis (Diehl, 2017). NASH occurs in approximately 20% of cases of NAFLD and is projected to increase to 27% of NAFLD cases in the US by 2030 (Estes, 2018). Approximately 20% of NASH patients will progress to cirrhosis, with potential complications of portal hypertension and hepatocellular carcinoma (Diehl, 2017). The stage of fibrosis is the most important determinant of mortality in patients with advanced NASH (Hagström, 2017). Patients with NASH and intermediate fibrosis (Stage 2) or advanced fibrosis (ie, Stage 3 and Stage 4 fibrosis) are at a higher risk for liver-related complications and mortality over a relatively short time scale (Sanyal, 2015, Hagström, 2017).

Dietary changes and lifestyle modifications are considered first-line interventions for patients with NASH. Treatments are primarily directed towards improving the metabolic parameters that contribute to disease pathogenesis, such as weight loss and exercise, reducing insulin resistance, and improving diabetic control. Pharmacological options for NASH are outlined in clinical practice guidance or guidelines (European Association for the Study of the Liver [EASL], 2016; Chalasani, 2018). While no firm recommendations are offered, both pioglitazone and vitamin E are suggested treatment options. Treatment with vitamin E or pioglitazone leads to improvement or trends in improvement, respectively, in NASH and both agents are associated with benefits on steatosis and reduction in serum alanine and aspartate aminotransferase levels (Sanyal, 2010). Weight gain is the most common side effect associated with pioglitazone and accelerated bone loss has been reported in women (Chalasani, 2018). Other treatment options that can be considered in individual patients are bariatric surgery, which can lead to improvement or resolution of NASH, and liver transplantation in patients with NASH and end-stage liver disease (EASL, 2016; Chalasani, 2018). NASH is now the most rapidly growing indication for liver transplantation in the United States (Parikh, 2017). Especially in light of the increasing prevalence of NASH, there is an urgent unmet medical need for specific treatments, with a focus on developing treatments that can decrease the progression of NASH and prevent or reverse fibrosis that accompanies NASH.

[figure not shown]
1.2. Compound Background

CC-90001 (also known as CC0491359) is a potent and selective inhibitor of c-Jun N-terminal kinase (JNK)

[figure not shown]

[figure not shown]

[figure not shown]

1.3. Rationale

1.3.1. Study Rationale and Purpose

NASH patients who have liver fibrosis comprise the group of patients with both a higher unmet need and potentially reversible disease, given the liver's capacity for regeneration.

Data from pre-clinical models [REDACTED]

[REDACTED] support that CC-90001 is potentially effective in patients with NASH and fibrosis. In addition, results from a Phase 2 study of selonsertib, which targets apoptosis signal-regulating kinase 1 (ASK1), provides preliminary evidence that treatment with an anti-inflammatory/anti-fibrotic agent may result in benefits on fibrosis in patients with NASH (Loomba, 2018). Since ASK1 is upstream of the JNK pathway (Win, 2018), CC-90001 as JNK inhibitor may also be an effective treatment in patients with NASH and advanced fibrosis.

The purpose of this study is to evaluate the efficacy and safety of CC-90001 in NASH subjects with either Stage 2 or Stage 3 fibrosis. It is expected that the results from this study will demonstrate a treatment-related difference in the proportion of Stage 2 or Stage 3 subjects who achieve a ≥ 1 stage improvement in liver fibrosis score at Week 52.

1.3.2. Rationale for the Study Design

CC-90001-NASH-001 is a Phase 2, double-blind, placebo-controlled, multicenter study to evaluate the efficacy and safety of CC-90001 in subjects with NASH and liver fibrosis. Efficacy evaluation will be based on liver biopsy-based endpoints [REDACTED].

Liver biopsy is widely considered as the “gold standard” for assessing fibrosis in NASH and has been validated in a large cohort of NASH patients (Kleiner, 2005). The primary efficacy endpoint will be the proportion of Stage 2 or Stage 3 subjects who achieve a ≥ 1 stage improvement in liver fibrosis score. The primary efficacy endpoint will be evaluated at Week 52 to allow slowly reversible subjects the opportunity to demonstrate a treatment benefit. Other liver biopsy-based endpoints, such as Non-alcoholic Fatty Liver Disease Activity Score (NAS) for evaluation of steatohepatitis and combination assessment of liver fibrosis score and steatohepatitis will be assessed as key secondary efficacy evaluations.

[REDACTED]

Laboratory evaluations, AEs, vital signs, electrocardiograms (ECGs), pregnancy tests and physical examinations will be monitored during the study to evaluate safety.

1.3.3. Rationale for Dose, Schedule and Regimen Selection

The efficacy and safety of 100 mg, 200 mg and 400 mg PO QD doses of CC-90001 will be evaluated in this study. [REDACTED]

2. STUDY OBJECTIVES AND ENDPOINTS

Table 1: Study Objectives

Primary Objective
The primary objective of the study is to evaluate the effect of oral CC-90001, administered once daily (QD), compared with placebo, on liver histology in subjects with nonalcoholic steatohepatitis (NASH) and Stage 2 or Stage 3 fibrosis.
Secondary Objective(s)
The secondary objectives are: 
• To evaluate the effects of oral CC-90001, administered QD, compared with placebo, in subjects with NASH and Stage 2 or Stage 3 fibrosis, on:
- Additional liver biopsy-based endpoints- Liver biochemistry-based endpoints- Metabolic parameters-based endpoints- Dose response- Safety and tolerability- Pharmacokinetics (PK)

Table 2: Study Endpoints

Endpoint	Name	Description	Timeframe
Primary	Liver fibrosis score	Proportion of subjects who achieve a ≥ 1 stage improvement in liver fibrosis using the nonalcoholic steatohepatitis (NASH) clinical research network (CRN) Histological Scoring System	Week 52
Secondary	Combined assessment of liver fibrosis score and steatohepatitis	Proportion of subjects who achieve a ≥ 1 stage improvement in liver fibrosis and no worsening of steatohepatitis (no worsening of lobular inflammation or hepatocellular ballooning score)	Week 52
	Nonalcoholic fatty liver disease (NAFLD) activity score (NAS)	Proportion of subjects with an improvement of ≥ 2 points in the total NAS in more than one category of steatosis, lobular inflammation, and hepatocellular ballooning, and no worsening of liver fibrosis	Week 52
	Resolution of NASH	Proportion of subjects who demonstrate absence of ballooning, and lobular inflammation score of 0 or 1	Week 52
	Resolution of NASH without worsening of liver fibrosis	Proportion of subjects who demonstrate absence of ballooning, and lobular inflammation score of 0 or 1 and no worsening of liver fibrosis	Week 52
	Progression to cirrhosis	Proportion of subjects who progress to cirrhosis	Week 52
	Liver biochemistry	Change from Baseline in serum aspartate aminotransferase (AST), alanine aminotransferase (ALT) and γ -glutamyl transferase (GGT)	through Week 52
	Metabolic parameters	Change from Baseline in total cholesterol, low density cholesterol (LDL) high density cholesterol (HDL), and triglycerides	through Week 52
	Dose response	Dose-related changes in the primary and secondary endpoints	through Week 24 (secondary endpoints); through Week 52 (primary and secondary endpoints)

Table 2: Study Endpoints (Continued)

Endpoint	Name	Description	Timeframe
Secondary	Safety	Type, frequency, severity, and relationship of adverse events (AEs) to CC-90001; Laboratory, 12-lead electrocardiogram (ECG), physical examination or other changes and tolerability	through End of Study
	Pharmacokinetics (PK)	Maximum plasma concentration of drug (C_{max}), area under the plasma concentration time-curve (AUC), time to peak (maximum) plasma concentration (T_{max}), terminal half-life ($t_{1/2}$), apparent total body clearance of the drug (CL/F), apparent volume of distribution (V_z/F), and accumulation index of CC-90001	Day 1 and Week 4

3. OVERALL STUDY DESIGN

3.1. Study Design

This is a Phase 2, randomized, double-blind, placebo-controlled, multicenter, multinational, dose-finding study evaluating the efficacy of treatment with CC-90001, compared with placebo, in NASH subjects with Stage 2 or Stage 3 fibrosis. Safety, PK, [REDACTED] of CC-90001 compared to placebo will be evaluated.

This study is designed to assess response to treatment on measures of fibrosis (liver biopsy, [REDACTED]), [REDACTED] liver biochemistry, and other efficacy parameters. It will also assess dose response and overall safety.

[figure not shown]
Subjects who sign ICF prior to the implementation of Protocol Amendment 4 and elect not to participate in the active treatment phase, or subjects who sign ICF after the implementation of Protocol Amendment 4 ([Figure 1](#)):

- Screening Phase: up to 10 weeks
- Double-blind Placebo-controlled Treatment Phase: 52 weeks
- Post-treatment Observational Follow-up Phase: 4 weeks

Subjects who sign ICF prior to the implementation of Protocol Amendment 4 and elect to participate in the active treatment phase ([Figure 1](#)):

[figure not shown]
- Screening Phase: up to 10 weeks
- Double-blind Placebo-controlled Treatment Phase: 52 weeks
- Double-blind Active Treatment Phase: 50 weeks
- Post-treatment Observational Follow-up Phase: 4 weeks

Figure 1: Overall Study Design
After the implementation of Protocol Amendment 4:

Note: The subjects who were previously randomized to the 100 mg dose group will remain in the 100 mg dose group throughout the study. It is expected that approximately 10-15 subjects will have been randomized to the 100 mg group at time of implementation of Protocol Amendment 4.

Prior to the implementation of Protocol Amendment 4:

EOF = end of follow-up; EOT = end of treatment; PO = oral; QD = once daily.

Approximately 180 adult male and female subjects with a confirmed diagnosis of NASH and Stage 2 or Stage 3 fibrosis based upon the NASH Clinical Research Network (CRN) Histologic Scoring System and a NAS of 4 or higher, with a score of at least 1 for each of the three components (steatosis, hepatocellular ballooning, and lobular inflammation), will be randomized 1:1:1 to treatment with oral CC-90001 (200 mg QD, 60 subjects; 400 mg QD, 60 subjects) or matching placebo (60 subjects) for 52 weeks. Prior to the implementation of Protocol Amendment 4, subjects were also randomized into a 100 mg QD dose group. The subjects who were previously randomized to the 100 mg dose group will remain in the 100 mg dose group throughout the study. It is expected that approximately 10-15 subjects will have been randomized to the 100 mg group at time of implementation of Protocol Amendment 4. Thus, a total of approximately 195 subjects will participate in the study.

Randomization will be stratified by liver fibrosis stage (Stage 2/Stage 3) and by the presence of Type 2 Diabetes Mellitus (DM) (yes/no). Approximately 60 subjects with Stage 2 or Stage 3 fibrosis will be enrolled per treatment arm. To ensure enrollment of a suitable number of subjects with Stage 3 fibrosis, up to 15 subjects with Stage 2 fibrosis may be enrolled per arm. Randomization to one stratum will be halted once the enrollment target is achieved for that stratum. Randomization, treatment assignment and stratification will be managed by an interactive web response system (IWRS).

An independent external data monitoring committee (DMC) will be responsible for review of the interim analyses data and will make recommendations to the Sponsor, who will be responsible for final decision-making. An unblinded interim analysis will be performed after approximately 50% of subjects complete 52 weeks of the placebo-controlled treatment phase (as described in the DMC Charter). The DMC will review the totality of the available data to determine the following options:

- Continue the study as planned
- Terminate the study for futility
- Stop enrolling a treatment arm due to futility if not fully enrolled at interim analysis

Subjects who sign informed consent form (ICF) prior to the implementation of Protocol Amendment 4 will have an option to participate in a double-blind active treatment phase. After 52 weeks of placebo-controlled treatment all placebo subjects will be re-randomized 1:1 by IWRS to the 200 mg QD or 400 mg QD dose groups at Week 54. Prior to the implementation of Protocol Amendment 4, subjects were also re-randomized into a 100 mg QD dose group. The subjects who were previously re-randomized to the 100 mg dose group will remain in the 100 mg dose group. Subjects who were initially randomized to active treatment arms will remain in their assigned dose groups through the end of the active treatment phase.

Subjects who sign ICF after the implementation of Protocol Amendment 4 will receive treatment in a double-blind placebo-controlled treatment phase only.

Subjects will have regularly scheduled visits to assess efficacy, safety, tolerability, [REDACTED] PK [REDACTED]; refer to [Table 3](#), Table of Events.

All subjects who discontinue prematurely from the study at any time will be required to enter the 4-week Post-treatment Observational Follow-up Phase.

The study will be conducted in compliance with the International Council for Harmonisation (ICH) of Technical Requirements for Registration of Pharmaceuticals for Human Use/Good Clinical Practice (GCP) and applicable regulatory requirements.

3.2. Study Duration for Subjects

Subjects who sign ICF prior to the implementation of Protocol Amendment 4 and elect not to participate in the active treatment phase, or subjects who sign ICF after the implementation of Protocol Amendment 4:

Subjects will participate for a maximum of 66 weeks in this study, which includes an up to 10-week Screening Phase; a 52-week Double-blind Placebo-controlled Treatment Phase; and a 4-week Post-treatment Observational Follow-up Phase.

Subjects who sign ICF prior to the implementation of Protocol Amendment 4 and elect to participate in the active treatment phase:

Subjects will participate for a maximum of 116 weeks in this study, which includes an up to 10-week Screening Phase; a 52-week Double-blind Placebo-controlled Treatment Phase; a 50-week Double-blind Active Treatment Phase; and a 4-week Post-treatment Observational Follow-up Phase.

3.2.1. Early Termination Visit

The Early Termination (ET) Visit is based on the subject's withdrawal from the study prior to the Week 102 Visit for subjects who participate in the active treatment phase or prior to the Week 52 Visit for subjects who do not participate in the active treatment phase. In addition, the Investigator may discontinue the subject from the study at any time based on his/her assessment of clinical efficacy and/or safety. The decision to discontinue a subject remains the responsibility of the treating physician and will not be delayed or refused by the sponsor. When a subject withdraws or is discontinued from the study treatment, every effort should be made to complete as many safety and efficacy assessments as reasonably appropriate. Refer to the Table of Events ([Table 3](#)) for the assessments to be performed at the ET Visit. The ET Visit should be scheduled as soon as possible after the decision is made to permanently discontinue study treatment.

3.2.2. Lost to Follow-up

Subjects will be considered lost to follow-up when they fail to attend study visits without stating an intention to withdraw from the study. The Investigator should show due diligence by documenting in the source documents the steps taken to contact the subject through multiple telephone calls and/or emails and one registered letter. After all reasonable attempts have been made to contact the subject, the subject should be recorded as "lost to follow-up" in the electronic case report form (eCRF).

3.3. End of Trial

The End of Trial is defined as either the date of the last visit of the last subject to complete the post-treatment follow-up, or the date of receipt of the last data point from the last subject

that is required for primary, secondary [REDACTED] analysis, as prespecified in the protocol, whichever is the later date.

4. STUDY POPULATION

4.1. Number of Subjects

Approximately 195 subjects with NASH and Stage 2 or Stage 3 liver fibrosis will be randomized worldwide.

4.2. Inclusion Criteria

Subjects must satisfy the following criteria to be enrolled in the study:

1. Subject is male or female ≥ 18 years of age at the time of signing the informed consent form (ICF).
2. Subject must understand and voluntarily sign an ICF prior to any study-related assessments/procedures being conducted.
3. Subject is willing and able to adhere to the study visit schedule and other protocol requirements.
4. Diagnosis of NASH with presence of Stage 2 or Stage 3 fibrosis based upon central reading of the NASH CRN Histologic Scoring System and a NAFLD Activity Score (NAS) of 4 or higher, with a score of at least 1 for each of the three components (steatosis scored 0 to 3, ballooning degeneration scored 0 to 2, and lobular inflammation scored 0 to 3) within 6 months prior to Screening or at Screening.
5. If histopathological specimens are submitted from a historical liver biopsy, the subject could not be on a therapy specifically for the treatment of NASH after liver biopsy and the subject's weight must have been documented to be stable since the liver biopsy (ie, within 5% if the liver biopsy was obtained 4 to 6 months prior to Screening or within 2.5% if the liver biopsy was obtained less than 4 months prior to Screening).
6. If receiving any of the following agents, the doses must have been stable for 3 months prior to Screening and the subject must agree to maintain stable doses during the course of the study, unless required to adjust doses due to safety reasons: ursodeoxycholic acid, fibric acid derivatives (fibrates) (eg, gemfibrozil), metformin, sodium-glucose co-transporter 2 (SGLT2) inhibitors (eg, canagliflozin), dipeptidyl peptidase-4 inhibitors ('gliptins') (such as sitagliptin), glucagon peptide-1 (GLP-1) agonists (eg, liraglutide), anti-obesity medications (eg, orlistat, lorcaserin, liraglutide, phentermine-topiramate, or naltrexone-bupropion). Note: If historical liver biopsy is submitted, the doses of above medications must have been stable for 3 months prior to biopsy and stable doses should be maintained through screening and during the course of the study. If SGLT2 inhibitors, GLP-1 agonists and anti-obesity medications have been recently discontinued, the treatment must have been stopped for at least 3 months prior to Screening or historical biopsy used for Screening assessment.
7. If receiving thiazolidinediones (eg, pioglitazone) or vitamin E, the doses must have been stable for 3 months prior to Screening and the subject must agree to maintain stable doses during the course of the study. Note: If historical liver biopsy is

submitted the doses of above medications must have been stable for 3 months prior to biopsy and stable doses should be maintained through screening and during the course of the study. If thiazolidinediones (eg, pioglitazone) or vitamin E have been recently discontinued, the treatment must have been stopped for at least 3 months prior to Screening or historical biopsy used for Screening assessment.

8. Females of childbearing potential (FCBP) ¹must:
- a. Have two negative pregnancy tests as verified by the Investigator prior to starting investigational product (IP). She must agree to ongoing pregnancy testing during the course of the study, and after end of study treatment. This applies even if the subject practices true abstinence* from heterosexual contact.
 - b. Either commit to true abstinence* from heterosexual contact (which must be reviewed on a monthly basis and source documented) or agree to use two forms of effective birth control (one of which is highly effective) at the same time, and be able to comply with, effective contraception without interruption, 28 days prior to starting IP, during the study therapy (including dose interruptions), and for 28 days after discontinuation of IP.

Approved options for birth control are:

- Any one of the following highly effective methods: Hormonal contraception (for example, birth control pills, intravaginal ring, transdermal patch, injection, implant); intrauterine device (IUD); tubal ligation (tying your tubes); or a partner with a vasectomy.

Note: Certain drugs may reduce the effectiveness of hormonal contraceptives during and up to one month after discontinuation of these concomitant therapies.

- Any effective method, for example, condoms.

9. Male subjects must:

Practice true abstinence* (which must be reviewed on a monthly basis) or agree to use a latex condom or nonlatex condom not made out of natural (animal) membrane (eg, polyurethane) during sexual contact with a pregnant female or a female of childbearing potential while participating in the study, during dose interruptions and for at least 28 days following IP discontinuation, even if he has undergone a successful vasectomy.

*True abstinence is acceptable when this is in line with the preferred and usual lifestyle of the subject. (Periodic abstinence [eg, calendar, ovulation, symptothermal, post-ovulation methods] and withdrawal are not acceptable methods of contraception).

¹ A female of childbearing potential is a sexually mature female who 1) has not undergone a hysterectomy (the surgical removal of the uterus) or bilateral oophorectomy (the surgical removal of both ovaries) or 2) has not been postmenopausal for at least 24 consecutive months (that is, has had menses at any time during the preceding 24 consecutive months).

4.3. Exclusion Criteria

The presence of any of the following will exclude a subject from enrollment:

1. Subject has any significant medical condition, laboratory abnormality (other than NASH related dyscrasias), or psychiatric illness that would confound the ability to interpret data, prevent the subject from participating or place the subject at unacceptable risk if he/she were to participate in the study.
2. History or evidence of decompensated liver disease, including clinical ascites, hepatic encephalopathy, or variceal bleeding.
3. Hepatitis and fibrosis more likely related to etiologies other than NASH such as, but not limited to, alcoholic steatohepatitis, autoimmune hepatitis, hepatitis B virus (HBV) infection, hepatitis C virus (HCV) infection, primary biliary cirrhosis, primary sclerosing cholangitis, Wilson's disease, alpha-1-antitrypsin deficiency, hemochromatosis or iron overload, and drug-induced liver disease.
4. Hemoglobin A1c (HbA1c) \geq 9.5% at Screening.
5. Subject has evidence of worsening liver function based on two measurements of AST, ALT, alkaline phosphatase (ALP) and total bilirubin (TBL) during Screening period (refer to Section 6.1).
6. Subject has a QTcF > 450 msec.
7. Subject has a history of liver transplantation or subject is likely to have liver transplantation during the study.
8. Current or history of recreational drug abuse or significant alcohol consumption for a period of more than 3 consecutive months within 1 year prior to screening. Significant alcohol consumption is defined as more than 14 oz (420 mL) per week in females and more than 21 oz (630 mL) per week in males, on average (1 oz/30 mL of alcohol is present in one 12 oz/360 mL beer, one 4 oz/120 mL glass of wine, or a 1.5 oz/45 mL measure of 40% proof alcohol).
9. Subject has urine ethyl glucuronide (EtG) > 500 ng/mL at Screening.
10. Use of any drugs that are known to cause hepatotoxicity, such as, but not limited to, acetaminophen (paracetamol) at dosages of > 3 grams/day and niacin at dosages of > 2 grams/day within 2 weeks of randomization.
11. Receiving immunomodulator agents (eg, tumor necrosis factor [TNF] inhibitors), or cytokine inhibitors (eg, tofacitinib) within 3 months of Screening.
12. History of recurrent bacterial, viral, fungal, mycobacterial or other infections (including, but not limited to, atypical mycobacterial disease and herpes zoster), or any major episode of infection requiring either hospitalization or treatment with IV or oral antibiotics within 4 weeks of the Screening Visit and at any time during the Screening Phase, up through the first dose of IP. Additionally, in the case of prior SARS-CoV-2 infection, symptoms must have completely resolved and based on investigator assessment in consultation with the clinical trial physician, there are no

sequelae that would place the participant at a higher risk of receiving investigational treatment.

13. History of active or latent tuberculosis (TB), unless there is medical record documentation of successful completion of a standard course of treatment considered appropriate, based on local prevalence of multi-drug resistant TB and consistent with World Health Organization guideline

Note: If a subject has adequate documentation of successful treatment for either latent or active TB, the QuantiFERON-TB Gold test is not needed. Instead, a chest radiograph, obtained within the 12 weeks prior to Screening, without changes suggestive of active TB infection as determined by a qualified radiologist, will be sufficient to permit further participation in the study for these subjects. Documentation of adequate treatment for TB must be obtained prior to randomization.

14. Subject has had a household contact with a person with active TB and subject did not receive appropriate and documented prophylaxis for TB

Note: Household contact is a person who shared the same enclosed living space as the index case for one or more nights or for frequent or extended daytime periods during the 3 months before the start of current treatment.

15. History or positive screen for human immunodeficiency virus (HIV) infection or congenital or HIV-unrelated acquired immunodeficiencies (eg, common variable immunodeficiency [CVID]).

16. History or positive screen for hepatitis B (See [Appendix D](#)) and/or hepatitis C.

Note: A subject who is hepatitis C antibody (HCV Ab) positive must be excluded unless the subject has a history of HCV and sustained viral response (undetectable HCV ribonucleic acid [RNA]) for at least 2 years prior to Screening and have a negative HCV RNA at Screening.

17. History of cardiac valve replacement requiring chronic anticoagulation therapy

18. History of inflammatory bowel disease (IBD).

19. History of bleeding peptic ulcer or bleeding diverticular disease within the last 5 years.

20. Subjects with Type 1 DM.

21. History of malignancy within the last 5 years (exceptions: excised and cured basal/squamous cell skin carcinomas or cervical carcinoma in situ).

25. Pregnancy or lactation.
26. Subject has a known hypersensitivity to CC-90001 or any ingredient in the investigational product (IP).
27. Concurrent treatment with another IP, including through participation in an interventional trial for COVID-19. Prospective subjects may not participate in a concurrent IP study or have received an IP within 5 drug half-lives prior to screening.
28. Prior use of approved agents for treatment of NASH within 6 months prior to Screening or historical biopsy used for Screening.
29. Subject has a history of bariatric surgery (eg, gastroplasty, roux-en-Y gastric bypass) within 5 years prior to Screening or subject is likely to have bariatric surgery during the study.
30. Evidence of the following abnormal laboratory values at Screening:
 - Serum ALT ≥ 5 X upper limit of normal (ULN)
 - Serum AST ≥ 5 X ULN
 - Serum ALP ≥ 2 X ULN
 - Serum TBL ≥ 1.3 mg/dL, unless subject has a documented diagnosis of Gilbert's syndrome. Subjects with Gilbert's syndrome must have total bilirubin of $\leq 5 \times$ ULN, with direct bilirubin \leq ULN and no clinical or laboratory evidence of hemolysis
 - Serum albumin < 3.5 g/dL
 - Alpha-fetoprotein ≥ 200 ng/mL (*Note: Alpha-fetoprotein > 20 ng/mL should be discussed with Sponsor to review the evaluation of Hepatocellular Cancer [HCC]*)
 - Estimated glomerular filtration rate (eGFR) < 60 mL/min/1.73 m²
 - Hemoglobin < 10 g/dL
 - Platelet count $< 140,000/\text{mm}^3$
 - INR > 1.2
31. Subjects who have received live attenuated SARS-CoV-2 vaccine within 1 month prior to Screening or anticipate the need to be vaccinated with live attenuated vaccine during the study. Further, for subjects who received an investigational COVID-19 vaccine as part of a clinical trial prior to the Screening, enrollment must be delayed until the biologic impact of the vaccine is stabilized, as determined by discussion between the Investigator and the Clinical Trial Physician.

Subjects who have received a vaccine approved for Emergency Use Authorization may be considered for inclusion, after discussion with the Medical Monitor.

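### Exclusion criterion 8 gives a per-drink alcohol content that its own spirit figures contradict, so the weekly limit can be read as two cut-offs (1.67-fold apart for spirits at 40% by volume)

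*Combined protocol and SAP*

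**What the plan says.** Section 4.3, criterion 8, excludes subjects with "significant alcohol consumption for a period of more than 3 consecutive months within 1 year prior to screening". It defines significant consumption as "more than 14 oz (420 mL) per week in females and more than 21 oz (630 mL) per week in males", on average. A parenthesis then supplies a conversion: "1 oz/30 mL of alcohol is present in one 12 oz/360 mL beer", with "one 4 oz/120 mL glass of wine" and "a 1.5 oz/45 mL measure of 40% proof alcohol" given as equivalents. No strength is stated for the beer or the wine.

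The protocol does not define the unit anywhere else, and it does not say whether the weekly limit is to be applied as a count of drinks or as a volume of alcohol. Section 6.1 rules out waivers, so eligibility depends on the criterion as worded.

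Two neighbouring criteria also deal with alcohol. Criterion 3 excludes hepatitis and fibrosis more likely due to other causes, alcoholic steatohepatitis among them. Criterion 9 reads "Subject has urine ethyl glucuronide (EtG) > 500 ng/mL at Screening". Table 3 repeats the EtG test at Weeks 24 and 52.

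**The concern.** The limit is expressed as a volume, and the parenthesis is there to translate drinks into that volume. The spirit example is the only one that gives both a drink volume and a strength, so it can be checked from the page, and it fails. Once the conversion is wrong, the volume limit and the drink count no longer describe the same intake, and nothing in the sentence says which governs.

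Criterion 8 is the only visible rule that puts a quantity on drinking history, in a trial whose population is meant to have non-alcoholic disease. The study is multicenter and multinational, and the limit is printed in both ounces and millilitres. One site could count drinks and another could convert to millilitres of alcohol, each believing it had followed the protocol. At stake is whether the same patient is eligible at both sites, and how precisely the enrolled population can be described.

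**Working it through.** **Inputs, all from criterion 8:** weekly limits of 14 oz (420 mL) for females and 21 oz (630 mL) for males; stated content of 1 oz (30 mL) of alcohol per drink; drink sizes of 360 mL beer, 120 mL wine and 45 mL spirit; spirit strength given as 40% proof.

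**1. Unit conversions.** At 30 mL per oz: 14 × 30 = 420; 21 × 30 = 630; 12 × 30 = 360; 4 × 30 = 120; 1.5 × 30 = 45. All of these reproduce, so the ounce and millilitre figures are not the problem.

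**2. Alcohol per drink.** Alcohol volume = drink volume × strength.
- Spirit, reading the strength as 40% by volume: 45 × 0.40 = 18 mL, against the stated 30 mL.
- Spirit, reading proof literally (assumption: the US scale, on which 40 proof is 20% by volume): 45 × 0.20 = 9 mL, which is further away.

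The stated 30 mL is not reproduced on either reading.

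**3. Strength needed to hold 30 mL.**
- Spirit: 30/45 = 66.7%
- Wine: 30/120 = 25%
- Beer: 30/360 = 8.3%

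**4. The two cut-offs, for spirits at 40% by volume.**

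| | Drink count (limit ÷ 30 mL) | Actual alcohol (limit ÷ 18 mL) | Ratio |
|---|---|---|---|
| Females | 420/30 = 14 | 420/18 = 23.3 | 1.67 |
| Males | 630/30 = 21 | 630/18 = 35 | 1.67 |

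Put the other way, 14 measures hold 14 × 18 = 252 mL of alcohol and 21 hold 21 × 18 = 378 mL, well short of 420 and 630 mL.

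**5. Who falls between them, in whole measures per week.** The criterion excludes intake above the limit.
- Females: the drink count excludes from 15. By volume, 23 × 18 = 414 mL is within the limit and 24 × 18 = 432 mL is over it. The readings disagree from 15 to 23.
- Males: the drink count excludes from 22. By volume, 35 × 18 = 630 mL is at the limit and not over it, and 36 × 18 = 648 mL is over. The readings disagree from 22 to 35.

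**6. Sensitivity.**
- Literal proof: 420/9 = 46.7 and 630/9 = 70 measures, a ratio of 30/9 = 3.33.
- Beer (assumed 4% to 6%, not in the documents): 14.4 to 21.6 mL per drink, ratio 2.1 down to 1.4.
- Wine (assumed 11% to 15%, not in the documents): 13.2 to 18 mL per glass, ratio 2.3 down to 1.7.

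**The case against.** The best defence is that the criterion carries its own counting rule. The parenthesis assigns one ounce to each named drink and the limits are 14 and 21 ounces, so a site that simply counts drinks gets 14 or 21 whatever the beverage, and the faulty content figure never enters. The volume reading requires a site to set aside the printed conversion and, for beer and wine, to supply strengths that the protocol does not give. Nothing shows that any site would do this. This stands: divergence between sites is possible, not established.

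The defence does not make the conversion correct, however, and it does not identify the governing part of the sentence. The limit itself is a volume in millilitres, so a reader who knows that a spirit measure does not contain 30 mL of alcohol has a fair reason to calculate.

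It is also fair to say that criterion 8 does not work alone. Criterion 3 excludes disease more likely to be alcoholic in origin, and criterion 9 excludes on urine EtG at Screening whatever intake is reported. Both reduce the practical effect. Neither replaces the weekly limit: criterion 3 gives no quantity, and criterion 9 is a test at Screening, whereas criterion 8 looks back over the preceding year.

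A reader might infer more: that heavier drinkers will be enrolled and that the histology endpoint will be blurred as a result. The documents do not support that. They give no distribution of drinking from which to count the patients in the disputed band, and no figure linking such intake to fibrosis response.

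**Conclusion.** The stated content of 30 mL per drink is wrong for the spirit example on the document's own numbers, and criterion 8 can therefore be read as two different limits. For spirits at 40% by volume these are 14 against 23.3 measures a week in females and 21 against 35 in males, a factor of 1.67.

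That factor should not be taken as a general one for the weekly limit. It rests on reading the strength as 40% by volume and applies to spirits only; the figures for other beverages depend on strengths that the documents do not give. Nor is everyone in the 15 to 23 or 22 to 35 band misclassified. The disagreement arises only between sites that read the criterion differently, and only for intake lasting more than 3 consecutive months within the year before screening.

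The consequence is limited to consistency of eligibility between sites and clarity of the population definition. Eligibility is settled before double-blind randomization, so inconsistent application does not in itself favour an arm, and no sample size, power or type I error figure depends on this criterion. It should still be corrected, because it is a wrong figure inside an eligibility threshold to which no waiver applies.

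**What to change.** Reword criterion 8 so that the weekly limit, the alcohol content per drink and the spirit strength define a single cut-off in a single unit, either drinks per week or a quantity of alcohol per week. Replace the 40% proof wording with an unambiguous strength. If drink equivalents are kept, give the strength assumed for each beverage so that the conversion can be checked. The sponsor has to state which cut-off was intended; the documents do not settle it, and this review does not choose one.

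The cost is a correction of about one sentence in Section 4.3. No analysis, sample size or assessment schedule changes.
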